5.6. Imputation of Partial Dates

Appendix 1 details partial date conventions for AEs and medications.

Treatment End Date

Missing treatment end dates will not be imputed at the end of the study. However, due to ongoing reporting needs, treatment end date will be imputed as earliest of the data cutoff date, date of death, or last treatment date recorded on the exposure eCRF.

End of Study Date

Missing end of study dates will not necessarily be imputed at the end of the study. However, due to ongoing reporting needs, end of study dates will be imputed as the earliest of the data cutoff date, date of death, or last date recorded on the eCRF.

5.7. Multiple Assessments and Visit Windows

If there are multiple assessments at a scheduled visit, then the last assessment will be used in the analysis.

Nominal visits (e.g., those identified by the study eCRF) will be the basis of summarization and statistical analysis; visit windows for each scheduled visit can be found in the Schedule of Activities from the protocol. Unscheduled data may be included in summaries of baseline and maximum/minimum change values; summaries of specific abnormalities any time post-baseline; and patient data listings.

Sponsor: Boston Pharmaceuticals, Inc.
Protocol Number: BOS-589-201
Version and Date: Version 1.2 12NOV2020

5.8. Lost to Follow Up or Lapse of Adequate Assessments

A patient will be considered lost to follow-up if he or she repeatedly fails to return for scheduled visits and is unable to be contacted by the study site staff. Missing evaluations will not be imputed.

5.9. Cohort Display

Cohorts will be displayed with the following columns. See the mock shells for additional details and a visual representation of the cohort display.

- 200 mg BOS-589 bid
- 50 mg BOS-589 bid
- Active Treatment (Combined 200 mg and 50 mg Cohorts)
- Placebo bid
- Overall (not needed for efficacy outputs)

For primary efficacy analyses testing, cohort significant p-values will be displayed in the hierarchical order below. Following the first p-value, each subsequent p-value will only be displayed if the prior p-value is < 0.05 .

- Active Treatment (Combined 200 mg and 50 mg Cohorts) vs. Placebo
- 200 mg BOS-589 bid vs. Placebo
- 50 mg BOS-589 bid vs. Placebo
- 200 mg BOS-589 bid vs. 50 mg BOS-589 bid

5.10. Missing Data

Missing data imputations for efficacy endpoints are described in Section 7; AE and concomitant medication, ongoing end of treatment, and ongoing end of study are described in Section 5.6. Otherwise, missing data will not be imputed.

6. STUDY PATIENT DATA

6.1. Analysis Sets

- The Screened Analysis Set will include all patients who have signed an informed consent document.
- The Intention-to-Treat (ITT) Analysis Set will include all randomized patients.
- The Per Protocol (PP) Analysis Set will include all patients in the ITT Analysis Set who received at least 1 dose of study drug and did not have any major protocol deviations.
- The Safety (SAF) Analysis Set will include all patients who received at least 1 dose of study drug.

Sponsor: Boston Pharmaceuticals, Inc.
Protocol Number: BOS-589-201
Version and Date: Version 1.2 12NOV2020

All safety analyses will be performed in the SAF Analysis Set by the actual cohorts. All efficacy analyses will be performed in the ITT and PP Analysis Sets by the randomized cohorts. Summaries of the Screened Analysis Set will be performed by the randomized cohorts.

The criteria for inclusion in the PP Analysis Set will be finalized and documented before database is locked and study unblinding. Additional information on inclusion into this population can be found in Section 6.3.

6.2. Patient Disposition

A summary of patient enrollment by site will be presented by cohort and overall for the Screened Set. The overall patient enrollment status (screened [i.e., consented], screen failures, randomized) will be provided. Patients who sign the ICF and are randomized but do not receive the study drug may be replaced. Once randomized, patients who are withdrawn from therapy before completing 28 days of dosing or are discontinued from the study for any reason will not be replaced.

Disposition data will be summarized for the Screened Set. The number of patients in each analysis set (ITT, SAF, PPS), completed treatment, with ongoing treatment, completed the study, and still ongoing in the study, will be summarized. The number of patients who discontinued study drug including reasons, the duration on study drug, and duration on study will be summarized. The number of patients who discontinued the study including reasons, the duration on study drug, and duration on study will also be summarized. Data will be presented by cohort and overall by assigned treatment.

A by-patient listing of patient enrollment data as well as a by-patient listing of patient disposition data including reason for treatment and study discontinuation will be presented for the screened patients.

6.3. Protocol Deviations

Protocol deviations will be recorded in the clinical trial management system.

Protocol deviations will be identified and classified as major protocol deviations prior to database lock and final unblinding. Major deviations are those deviations that significantly impact efficacy and result in the removal of patients from the PP Analysis Set. Major protocol deviations may include but are not limited to:

- Violation of Inclusion/Exclusion Criteria
- Study drug compliance $\leq 80\%$ or $\geq 105\%$
- Use of prohibited therapies
- Incorrect treatment

Major protocol deviations will be summarized by cohort and deviation category. Protocol deviations will be listed for the ITT Analysis Set by assigned treatment.

6.4. Demographic, Baseline Characteristics, and Disease History

Patient demographics and baseline characteristics will be summarized by cohort and overall for the ITT Analysis Set by assigned treatment. These will include age, sex (Male, Female), gender (Male, Female, Transgender Female to Male, Transgender Male to Female, Not willing to respond, Other), childbearing potential for females (Yes, No), ethnicity (Hispanic or Latino, Not Hispanic or Latino), race (White, Black or African American, Asian, American Indian or Alaska Native, Native Hawaiian or Other Pacific Islander), height (cm), weight (kg), and body mass index (BMI; kg/m²). BMI will be calculated as (weight in kg) / (height in m)².

Demographics and baseline characteristics will be listed for the ITT Analysis Set.

Disease history will be summarized by cohort and overall for the ITT Analysis Set by assigned treatment. These will include frequency of pain in the last 3 months, how often this pain happens close in time to a bowel movement, how often when the pain happens are stools softer or harder than usual, how often when the pain happens are stools more frequent or less frequent than usual, how often the pain gets worse with menstrual bleeding for females, how often the pain gets worse after a meal, how often the pain limit usual activities, if the pain is continuous or not, if the pain has lasted for over 6 months or not, and abnormal stool condition. These are all collected from eCRF.

Disease history data will be listed for the ITT Analysis Set in by-patient listings.

6.5. Medical History

Medical history will be summarized by Medical Dictionary for Medical Affairs (MedDRA) system organ class (SOC) and preferred term (PT). Sort order will be by descending overall incidence of SOC followed by descending incidence of overall PT. Medical history will be summarized and presented by cohort and overall for the SAF by actual treatment.

Medical history will be presented in data listings for the SAF Analysis Set. Medical history coded terms will be provided, including the SOC and PT per MedDRA. The data management plan specifies the version of MedDRA used for medical history coding.

6.6. Prior and Concomitant Medication

The incidence of medication use will be summarized by the World Health Organization (WHO) Drug Dictionary Anatomic Therapeutic Chemical (ATC) Level 2 classification (i.e., therapeutic main group) and preferred name. A patient will be counted only once at each level of reporting. Prior medications are those which have been identified to have been discontinued prior to the first dose of study drug (i.e., taken exclusively during the pre-treatment period). Concomitant medications are those which have been identified to have been taken at any point during the on-treatment period, including medications which started prior to first dose of study drug but are ongoing at first dose. The data management plan specifies the version of WHO Drug used.

Sponsor: Boston Pharmaceuticals, Inc.
Protocol Number: BOS-589-201
Version and Date: Version 1.2 12NOV2020

Partial dates will be imputed according to Appendix 1 for the determination of prior, concomitant, and subsequent medications.

Concomitant medication use will be summarized and presented by cohort and overall for the SAF Analysis Set by actual treatment. Prior medications will be summarized in a similar manner.

During the treatment period, patients may also take protocol-permitted loperamide rescue medication for the acute treatment of uncontrolled diarrhea. Rescue medications will be summarized in a similar manner as the concomitant medication.

All prior and concomitant data will be provided together in a by-patient listing including the verbatim and preferred drug name and WHO ATC Class (ATC Level 2) for the SAF. Prior and subsequent medications will be flagged by unique identifiers in the listing. Loperamide rescue medication use will also be flagged in the listing.

6.7. Rescue Medication

Rescue medication usage (loperamide) will be summarized by cohort and overall for all patients in the SAF Analysis Set. The time periods to be summarized will include the run-in period prior to Baseline/Day 1, the treatment period (Baseline/ Day1 through Day 29), and the post-treatment period (after Day 29 through Day 43). Categorical summaries will include the incidence of patients with rescue medication use at any time during the associated time period, as well as, the number of total doses of rescue medication used (0 doses, 1 dose, 2 doses, 3 doses, 4 doses, 5 doses, 6 doses, 7 doses, 8 doses, 9 doses, 10 or more doses) during the associated time period. The total number of doses of rescue medication also will be summarized as a continuous measure during the associated time period.

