5.1 Inclusion Criteria

In order to be eligible to participate in this study, an individual must meet all of the following criteria:

Age

1. Male and female patients must be 18 to 65 years of age, inclusive, at the time of signing informed consent.

Run-in eDiary Compliance

2. Patient has completed the daily electronic diary on at least 6 of the 7 days during the week prior to randomization AND at least 11 of the 14 days during the 2 weeks prior to randomization. Patients have up to 3 weeks to meet these criteria.

Type of Patient and Disease Characteristics

3. Patient meets the diagnosis of IBS based on the Rome IV diagnostic criteria (CCI [REDACTED]):*

- Recurrent abdominal pain occurring, on average, at least 1 day per week and associated with 2 or more of the following:
 - Related to defecation;
 - Associated with a change in frequency of bowel movements;
 - Associated with a change in form (appearance) of stool;

* These criteria must be fulfilled for the last 3 months prior to randomization and onset must have occurred at least 6 months prior to randomization.

4. Patient meets the diagnosis of IBS-D subtype based on Rome IV diagnostic criteria (CCI [REDACTED]). On days when the patient experiences IBS symptoms:

- At least 25% of stools are loose or watery; AND
- Fewer than 25% of stools are hard.

5. Over the final 7 days of the run-in period, the patient has an average of WAP scores in the prior 24 hours of 3.0 to 8.0 (on a 0 to 10 numerical rating scale, where 0 indicates no pain and 10 indicates worst pain imaginable).
6. Over the final 7 days of the run-in period, the patient has an average daily BSFS score ≥ 5.0 (on a 1 to 7 scale, where 1 = hard, lumpy stools, and 7 = watery, liquid stools), and there must be at least 2 days with stool consistency of Type ≥ 6 .
7. Patient is not planning to change his or her usual diet and lifestyle during the course of the study.

Diagnostic Assessments

8. Patient must undergo or previously have undergone (a) an appropriate evaluation for their IBS symptoms, including an evaluation for organic/structural etiologies (if in the presence of alarm symptoms); and (b) age-appropriate screening for colorectal cancer, if applicable.
 - a) If at least one of the following alarm features are present, then the patient must have had a colonoscopy that should include biopsy since the onset of symptoms or within the past 5 years (whichever is less):

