6.7.1 Rescue Medicine

During the double-blind Treatment Phase of the study, patients will be allowed to take loperamide rescue medication for the acute treatment of uncontrolled diarrhea. It is recommended that patients refrain from loperamide unless a minimum of 2 or more uncontrolled diarrhea events that cause significant discomfort and prevent normal everyday activities are experienced in a given 24-hour period.

If loperamide must be used, patients must not exceed the 2 mg (unit dose), which may be taken once approximately every 6 hours and must not exceed the following dosing requirements:

- No more than 4 unit doses over a continuous 24-hour time period (8 mg/day);
- No more than 7 unit doses over a continuous 48-hour time period (14 mg over 2 days);
- No more than 11 unit doses over a continuous 7-day time period.

The use of loperamide rescue medication should be recorded electronically.

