8.1 Study Periods

The study will comprise 3 phases:

1. **Pre-Treatment Phase** (up to 5 weeks), in which all patients will be assessed for eligibility. The pre-treatment phase will consist of initial screening assessments (Visit 1) and a Run-in period (Visit 2 through Visit 3).
2. A **Treatment Phase** (4 weeks), in which all patients will return to the clinical for randomization and start of treatment (Visit 3 – Day 1) followed by weekly visits (Visit 4 – Day 8 [\pm 1 day], Visit 5 – Day 15 [\pm 1 day], Visit 6 – Day 22 [\pm 1 day]) until Visit 7 – Day 29 (\pm 1 day), and
3. A **Follow-up Phase** (2 weeks), in which patients who complete Visit 7, will be asked to return for an End-of-Study Follow-up visit (Visit 8 – Day 43 [\pm 3 days]) for assessment of treatment outcome (e.g., safety, durability of effect).

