8.2 Screening Assessments

After signing the ICF(s), the patient will undergo the initial screening assessments and procedures as described in the Schedule of Activities (Section 1.3) to determine eligibility.

Eligible patients will enter the Run-in period. At the beginning of the Run-in period, patients will receive instructions for completing an electronic diary to collect daily information related to their IBS-D symptoms, their bowel function, and rescue medication use.

Patients who meet the following requirements will be eligible for participation and immediate randomization into the double-blind treatment phase (i.e., all diary conditions listed must be met to qualify for randomization):

- have completed the daily electronic diary on at least 6 of the 7 days during the week prior to randomization AND at least 11 of the 14 days during the 2 weeks prior to randomization
- over the final 7 days of the run-in period, the patient has an average of WAP scores in the prior 24 hours of 3.0 to 8.0 (on a 0 to 10 numerical rating scale, where 0 indicates no pain and 10 indicates worst pain imaginable),

- over the final 7 days of the run-in period, the patient has an average daily BSFS score ≥ 5.0 (on a 1 to 7 scale, where 1 = hard, lumpy stools, and 7 = watery, liquid stools), and there must be at least 2 days with stool consistency of Type ≥ 6 , and
- have not used any loperamide rescue medication in the 2 weeks prior to randomization

Eligible patients will be instructed to return to the study site for the Baseline visit on Day 1.

If patients do not meet all of the 4 diary conditions required for entry during the 2 week run-in period, the run-in may be extended for an additional week in accordance with investigator judgment (for a total run-in period of up to 3 weeks). Eligibility will then be based on the most recent 14 days of the extended run-in period.

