5.2. Reference Dates

Reference dates are defined as follows:

- Screening date is defined as the electronic case report form (eCRF) provided visit date on which a patient was screened for trial entry.
- Informed consent date is defined as the eCRF provided date of informed consent from the informed consent page.
- Run-in period start date is defined as earliest date of eCRF provided visit date from the Run-in period page.
- Run-in period end date is defined as eCRF provided date of randomization -1 from the randomization page.
- Treatment start date is defined as the date of first dose of any study drug.
- Treatment end date is defined as the date of last dose of any study drug.
- Age will come directly from the eCRF which is integrated from IWRS based on the informed consent date.

Sponsor: Boston Pharmaceuticals, Inc.
Protocol Number: BOS-589-201
Version and Date: Version 1.2 12NOV2020

- Safety data, such as AEs and laboratory assessments, will use the treatment start date as a reference date.
- Efficacy data will use the treatment start date as a reference date.
- Study day will be based on treatment start date as a reference date. Study Day 1 will be the day patients start the first dose of study drug.

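### SAP 6.7 summarises rescue loperamide without a denominator for diary days observed, so a cohort observed for less time can appear to use less rescue

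*SAP*

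**What the plan says.** SAP 6.7 sets the population: "Rescue medication usage (loperamide) will be summarized by cohort and overall for all patients in the SAF Analysis Set". It names three periods: the run-in, then "the treatment period (Baseline/ Day1 through Day 29), and the post-treatment period (after Day 29 through Day 43". Within each it plans the proportion with any use, categories of total doses from 0 to 10 or more, and a continuous summary: "The total number of doses of rescue medication also will be summarized as a continuous measure during the associated time period".

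On capture, Protocol 6.7.1 says "The use of loperamide rescue medication should be recorded electronically", and Protocol 8.3 places rescue use among the items entered in the daily electronic diary.

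SAP 6.7 sets no minimum number of diary days, does not divide by days observed, and does not say how a truncated period is treated. SAP 5.10 makes no imputation the default outside the situations it lists.

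Two nearby sections do account for observation time. SAP 6.8 divides tablets taken by the duration of exposure. SAP 7 averages daily diary scores over the non-missing days.

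**The concern.** A dose total depends on both the rate of use and the time observed. The Safety set requires only one dose of study drug, so it includes patients who leave early, and Protocol 9.2 expects some attrition. Post-treatment observation is also selective, because Protocol 8.1 describes that phase as one "in which patients who complete Visit 7, will be asked to return". A partly observed patient contributes a short-period total to a column labelled with the full period. The any-use proportion and the dose categories have the same weakness.

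Loperamide acts on stool consistency and frequency, both secondary endpoints, and SAP 7 has no rule for rescue use. A reader who wants to know whether rescue differed between BOS-589 and placebo will look at this table. If one cohort was observed for less time, part of any apparent difference in rescue would come from observation time alone.

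**Working it through.** There is no planned figure to reproduce, since the documents give no rescue rate and no dropout rate. Period lengths come from the documents. Rates and losses below are assumptions.

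**Inputs**
- Treatment period, Day 1 to Day 29: 29 days (SAP 6.7).
- Post-treatment period, Day 30 to Day 43: 14 days (SAP 6.7).
- True rate r, equal in all cohorts and constant over time; r = 0.25 doses per day for illustration.
- A fraction p of a cohort leaves the study on Day d; everyone else is observed for all 29 days.

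**One patient.** Expected total = r x days observed. Over 29 days this is 0.25 x 29 = 7.25 doses. Leaving on Day 7 gives 0.25 x 7 = 1.75 (7/29 = 24%). Leaving on Day 14 gives 3.5 (48%).

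**Cohort mean total** = r x [(1 - p) x 29 + p x d]. The rate cancels in the ratio between cohorts.

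| Dropout, cohort A against B | Day left | Mean days, A | Mean days, B | Ratio of mean totals |
|---|---|---|---|---|
| 10% against 10% | 7 | 26.8 | 26.8 | 1.00 |
| 20% against 10% | 7 | 24.6 | 26.8 | 0.92 |
| 30% against 10% | 7 | 22.4 | 26.8 | 0.84 |
| 20% against 10% | 14 | 26.0 | 27.5 | 0.945 |
| 30% against 10% | 14 | 24.5 | 27.5 | 0.89 |

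For the third row, A is 0.7 x 29 + 0.3 x 7 = 22.4, B is 0.9 x 29 + 0.1 x 7 = 26.8, and 22.4/26.8 = 0.84.

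**Diary gaps.** Missing a fraction m of days multiplies the expected total by 1 - m. Gaps of 10% and 20% reduce 7.25 to 6.53 and 5.80. If one cohort misses 20% and the other 10%, the ratio is 0.8/0.9 = 0.89.

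**With the cohort-level rate.** In the third row at r = 0.25, mean totals are 5.6 and 6.7 doses. The rates are 7 x 5.6/22.4 = 1.75 and 7 x 6.7/26.8 = 1.75 doses per week, so the spurious difference disappears.

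**The case against.** The strongest reply is that this is one untested descriptive table, and that bias between cohorts requires differential loss, which the documents give no reason to expect. That is right as far as it goes. The whole allowance above 120 is 12 of 132 patients, and it also covers a higher placebo rate. Spread evenly as 4 of 44, all leaving on Day 8, it lowers each mean by (4/44) x (1 - 8/29) = 6.6% and leaves the contrast unchanged. Stopping study drug is not leaving the study (Protocol 7.1), and the diary continues (Schedule of Activities, note h), so only withdrawal and diary gaps matter. SAP 6.2 and 6.8 already show duration on study and on drug by cohort. They do not show completed diary days.

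Four stronger readings are tempting, but the documents do not support them.

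- *Unequal period lengths make a steady user's rescue appear to rise on treatment and fall afterwards.* Treatment is 29/14 = 2.07 times as long as post-treatment, but SAP 6.7 plans no comparison between periods and the lengths are visible in its definitions. Run-in is not comparable in any case, because Protocol 8.2 requires no loperamide in the 2 weeks before randomization. A rate would not change that.
- *Patients who never enter follow-up are counted as 0 doses.* SAP 6.7 does not say so, and SAP 4 bases percentages on non-missing values with missing shown separately. The rule is unstated. The firm problem is the partly observed patient.
- *This is the trial's only comparison of rescue use, seen only through the diary.* SAP 6.6 also summarises rescue incidence by cohort, and Protocol 6.7 collects over-the-counter medicines with dates and dose. What SAP 6.7 alone provides is a tabulated dose quantity.
- *Diaries will miss about a fifth of days, because entry requires "at least 11 of the 14 days during the 2 weeks prior to randomization".* That is a run-in threshold. On treatment the diary is required daily, and a uniform loss cancels between cohorts.

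**Conclusion.** The concern holds in a limited form. The rescue measures in SAP 6.7 have no observed-day denominator, although the SAP uses one in 6.8 and 7. Where withdrawal or diary completion differs between cohorts, the less-observed cohort's use is understated within the treatment or post-treatment period. Under the assumed patterns above, the ratio of mean totals falls to between 0.84 and 0.945 when the true ratio is 1. Those figures assume a constant rate and leavers who use rescue like everyone else. If leavers are the heavier users, the understatement is larger. With equal loss it vanishes. No hypothesis test depends on this table and the primary analysis is unaffected, so this is a worthwhile refinement and not a flaw in the trial's main inference.

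**What to change.** In SAP 6.7, keep the totals, categories and any-use proportion, and add for the treatment and post-treatment periods, by cohort:

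- rescue rate = 7 x total loperamide doses / total completed diary days, with both sums taken over all patients in the cohort with at least one completed diary day in the period;
- the number of patients with any diary data in the period, and their mean number of completed diary days;
- a rule that a patient with no completed diary day in a period is shown as missing, not as 0 doses.

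Use the cohort-level ratio and not the mean of individual rates. With a one-day minimum, a patient with two doses on a single diary day would score 14 per week, above the protocol's own limit of 11 unit doses in 7 days.

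The cost is SAP wording and one derived variable, the count of completed diary days, from data already collected. No protocol amendment is needed. The rate corrects for time observed. It does not correct for leavers whose later use would have differed, and it describes the whole period, not specifically the week before Day 29.
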